PROTOCOL TITLE: Efficacy of a Coupler-Based Fitting Approach for Experienced Users Receiving Replacement Hearing Aids

PRINCIPAL INVESTIGATOR: [name], Au.D., Ph.D.

VERSION NUMBER AND DATE: Version 10, June 10, 2022

SPONSOR/FUNDING SOURCE: VA RR&D Merit Review C2777-R

Purpose

The overarching purpose of this project is to develop an accurate coupler-based fitting model for experienced hearing-aid users obtaining replacement hearing aids of any style that will result in positive patient outcomes while mitigating a face-to-face fitting visit.

The proposed project addresses three aims:

Specific Aim 1. Develop vent correction factors for testbox fittings of in-the-ear (ITE) and traditional behind the ear (BTE) with custom earmold hearing aids, which will be used to evaluate the real ear to complete difference (RECD)-fitting approach in a sample of experienced users receiving replacement hearing aids. Hypothesis 1a. RECD coupler-based fittings will accurately meet prescriptive targets and expected aided audibility for ITE and traditional BTE styles. Hypothesis 1b. Subjective outcomes from RECD coupler-based fittings will meet or exceed published norms.

Specific Aim 2. Develop correction factors for RECD coupler-based fittings of hearing aids with non-custom coupling (i.e., mini-BTEs with slim tubing and noncustom open canal coupling—open fits). Hypothesis 2. Correction factors will be developed to account for RECD coupler-based fittings with open canals.

Specific Aim 3. To determine if the open-fit RECD-fitting approach is equivalent to the standard of care (SoC) open-fit fitting approach. Hypothesis 3a. Derived REARs from open-fit RECD-fittings will accurately meet prescriptive targets and expected aided audibility and will be equivalent to in situ REARs in SoC fittings of open-fit styles. Hypothesis 3b. The subjective outcomes will not significantly differ between the experimental RECD-fitting group and the SoC group for open-fit styles.

Background and Significance

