1b-Hearing aid fittings and verification in VA. Veterans Health Administration (VHA) Handbook 1170.02 describes the scope of audiology and speech-language pathology services in VA, which is comprehensive in nature and promotes best practice. This proposal narrowly focuses on verification and validation of an experimental hearing aid fitting approach for experienced users. This experimental approach incorporates verification and validation specified by best practice, but in an alternative method. If the experimental fitting approach is effective and efficient, then it may be incorporated in VA practice for some Veterans, and be an additional service in the collection of comprehensive services available. Probe microphone real-ear measurements are the gold standard method of verifying real-ear hearing-aid performance to maximize aided audibility and ensure that the maximum output of the hearing aid does not exceed uncomfortable loudness levels of the patient (e.g., Mueller, 2001; Valente, Abrams, Benson, Chisolm, Citron, Hampton, & Sweetow, 2006). With in situ real ear aided response (REAR) measurements, the REAR is matched to a validated prescription derived from pure-tone thresholds referenced to the real-ear sound pressure level (SPL) in the patient's ear. Research shows that accurate fittings (i.e., a close match between hearing aid gain/REAR and prescription) result in improved speech intelligibility (quiet and noise) and better subjective outcomes relative to inaccurate fittings (Aazh & Moore, 2007; Abrams, Chisolm, McManus & McArdle, 2012; Baumfield & Dillon, 2001; Byrne & Cotton, 1988; Mueller, 2005; Moore, Alcántara, & Marriage, 2001). Thus, VA advocates the use of probe microphone measures when verifying hearing aid fittings.

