Study 3 will use a quasi-random design. Participants receiving replacement receiver in the canal (RIC) mini BTE hearing aids and will be randomly assigned to one of four groups based on hearing-aid coupling (open vs closed domes). The standard of care (SoC) group receiving open coupling (SoC-open) or closed coupling (SoC-closed) or the experimental group receiving the experimental (EXP) hearing aid service delivery approach (EXP-open or EXP-closed). The outcomes of the experimental fittings will be compared to the respective SoC fitting.

Risk/Benefit Assessment

The procedures used in the proposed study produce minimal risks. There are no known social, legal, physical, psychological, genetic or financial risks associated with participation. All participants in Study 1 or Study 3 will receive a standard, comprehensive hearing evaluation. Some participants may find this boring or may be frustrated when repeated words that might be difficult to hear or listen for soft beeps. This is a common clinical procedure that is not invasive. All participants in Study 1 or Study 3 will obtain a cognitive screening test. This screener may cause people to feel uncomfortable having to be asked to remember things or if they find the test difficult. All participants will receive in situ real-ear verification of hearing aid fitting(s). There may be slight discomfort during these measurements, but they should not be painful and they are routine, taking only a few minutes to complete for each ear.

Participants in Study 1 only will have earmold impressions made of their ears so custom replacement behind-the-ear and in-the-ear hearing aids can be ordered for each ear. There is a rare, but small chance of ear injury during this routine clinical procedure. All standard clinical safeguards associated with obtaining earmold impressions (otoscopy, use of otoblocks) will be used.

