Participants may directly benefit from this protocol. They all will receive a comprehensive audiologic evaluation and those results will be placed in their medical record. For those in Study 1 and 3, their current hearing aids will be evaluated to ensure proper function and best fit. If in need of repair, maintenance, or adjustment, these will be made. Their replacement hearing aids will be carefully fitted and verified to best practices and they will receive close follow-up regarding them. They may enjoy the benefit of obtaining hearing aids without having to come into the clinic for a face-to-face visit (experimental groups only). If the results between the SoC and experimental groups are equivalent, then this study would provide an evidence-based, RECD fitting approach that will improve Veteran-Centric care. Specifically, the RECD-based delivery model reduces the number of visits required to fit a replacement hearing aid compared to the SoC delivery model and, therefore, should result in greater patient satisfaction and reduced costs. In addition, the reduction in the number of clinic visits for established hearing aid patients may produce a reduction in wait times (greater access to care) for new patients seeking audiology services. The risks to participants is less than minimal and the anticipated benefits outweigh the minimal risk.

Selection of Subjects

Study 1 and Study 3: Inclusion Criteria:

Participants will be included in the study if the following criteria are met:

1. aged 18-85 years
2. experienced hearing-aid users who are obtaining replacement VA-issued hearing aids of the same style as their current hearing aids
3. competent hearing aid skills as demonstrated via the checklist (See appendix)
4. no more than a moderate sensorineural hearing loss (defined as less than or equal to 60 dB HL pure-tone average at 500, 1000, and 2000 Hz AU)
5. symmetrical hearing between the ears as defined as no more than a 20 dB difference in pure-tone thresholds at two consecutive frequencies
6. >/=50% word-recognition abilities in quiet as measured during the diagnostic audiologic evaluation

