Session 1 (Baseline, Pre-Fitting). The baseline testing for Session 1 of Study 3 is nearly identical to the procedures in Session 1 of Study 1. See Section 3g. Thus, only the minor differences will be described here. The comprehensive hearing evaluation, completion of the intake form (Appendix), and reorientation that is needed will be completed with the participant's current hearing aids. Their current hearing aids will be maintained and re-verified to ensure an accurate fit to prescriptive targets. The self-report outcome battery on the current hearing aids will be assessed (COSI, SADL, IOI-HA, and the aided portion 1 of the APHAB). Individual RECDs and REURs will be measured for each ear of each participant. The choice in replacement open vs closed domes will be made following routine clinical procedures. The receiver length will be measured and the dome size (open vs closed) will be estimated using manufacturer measurement tools. The replacement hearing aids will be ordered in ROES.

Session 2-The Intervention 'Visit'.

SoC-open and SOC-closed Group Fittings. These groups will receive the SoC, 30-minute face-to-face fitting appointment 4 weeks after Session 1, the average wait time for a fitting appointment. The right and left hearing aids will be programmed separately to the National Acoustics Laboratory Non-Linear 2 (NAL-NL2) prescription. The REAR of the hearing aids will be verified to the 50-, 65-, and 75-dB SPL prescriptive targets generated by the Verifit 2 system using the Speechmap™ stimulus. The criterion for an appropriate fitting would be ± 3 dB between the output and the prescriptive target from 250 Hz to the frequency in which the unaided threshold crossed the 65-dB SPL target. The real ear aided response for an 85 dB SPL input (REAR85) will be measured using an 85-dB SPL swept pure-tone to ensure that the maximum output of the hearing aids does not exceed the predicted uncomfortable loudness levels of the participant (feedback manager deactivated during this measurement only). The programming options will be optimized based on the information obtained on the intake form (Appendix). The participant will be provided with the manufacturer brochure and programming report from the manufacturer software. Consistent with current SoC, no orientation will be provided.

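### Study 3 promises an equivalence conclusion but plans and sizes only difference analyses, with no between-group margin or confidence-interval rule

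*Combined protocol and SAP*

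**What the plan says.** The objective is worded as equivalence. Specific Aim 3 reads: "To determine if the open-fit RECD-fitting approach is equivalent to the standard of care (SoC) open-fit fitting approach". Hypothesis 3a says that derived REARs from the experimental fittings "will be equivalent to in situ REARs in SoC fittings of open-fit styles". Hypothesis 3b turns to self-report: "The subjective outcomes will not significantly differ between the experimental RECD-fitting group and the SoC group for open-fit styles". Under Design, Study 3, the contrast is named: "The outcomes of the experimental fittings will be compared to the respective SoC fitting".

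Study 3 Data Analysis carries the Study 1 approach over to REAR. That approach is a generalized linear model of differences in dB, run separately for left and right ears. The section says this will establish whether in situ REARs of the two kinds of fitting are equivalent. For self-report it plans a mixed model repeated measures ANOVA, to see whether outcomes differ.

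Study 3 Power Analysis sizes the study for an ANOVA effect of eta-squared 0.10 at alpha 0.05 and power 0.95. This gives 152 ears, 76 participants, 19 per group, raised to 88 (22 per group) for attrition.

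Risk/Benefit Assessment states what follows from the result: "If the results between the SoC and experimental groups are equivalent, then this study would provide an evidence-based, RECD fitting approach".

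**The concern.** A difference test and an equivalence claim ask opposite questions. Failing to reject no difference is not evidence that a difference is small, and it becomes more likely as data get fewer or noisier. Hypothesis 3b makes that failure the predicted result, so a small or noisy study would favour it. For REAR the plan says an equivalence question will be answered, but the model named has no rule for answering it.

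At stake is the main conclusion of the project's only comparison with a randomised SoC group, which the Risk/Benefit Assessment treats as the evidence base for the RECD approach. The measurements planned can support an equivalence analysis. What is missing is the decision rule, and a margin chosen after the Session 3 data have been seen would carry little weight.

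**Working it through.** **1. Reproduce the plan's sample size.** Inputs from Study 3 Power Analysis: four groups, eta-squared 0.10, alpha 0.05, 100 ears for power 0.80 and 152 ears for 0.95. Take f² = 0.10/0.90 = 0.111 and noncentrality N × f², with a four-group omnibus F test (3 numerator df) and ears treated as independent.

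- N = 100: noncentrality 11.1, power 0.79 (stated 0.80).
- N = 152: noncentrality 16.9, power 0.94 (stated 0.95).

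The figures are reproduced closely, as the size needed to detect a difference. Eta-squared 0.10 is an effect to be found, not a margin.

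**2. Look for an equivalence rule.** Two dB figures come near.

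- Session 2 of Study 3: "The criterion for an appropriate fitting would be ± 3 dB between the output and the prescriptive target". This applies to each fitting against its own target, not to experimental minus SoC.
- Background section 1c mentions ±5 dB agreement in earlier research with custom earmolds. Study 3 does not adopt it.

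The repeat SoC REARs in Session 3 gauge measurement variability and help interpretation, but no rule follows from them. Nothing comparable exists for the self-report scales.

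**3. Illustrate self-report.** Two-sample t test, two-sided 0.05, one value per participant, n per group. Noncentrality = d × √(n/2), df = 2n − 2. The 0.5 SD effect and the baseline correlations r are assumptions. With baseline as covariate, d becomes 0.5/√(1 − r²) and one df is lost.

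| Case | d | noncentrality | P(non-significant) |
|---|---|---|---|
| 19 v 19, unadjusted | 0.50 | 1.54 | 0.68 |
| 22 v 22, unadjusted | 0.50 | 1.66 | 0.63 |
| 19 v 19, r = 0.5 | 0.577 | 1.78 | 0.59 |
| 19 v 19, r = 0.7 | 0.700 | 2.16 | 0.44 |
| 38 v 38, unadjusted | 0.50 | 2.18 | 0.42 |

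The last row pools open and closed couplings, which the plan does not state.

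Expected 90% interval half-width = t(0.95, df) × √(2/n), in SD units:

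- 19 v 19: 1.688 × 0.324 = 0.55.
- 38 v 38: 1.666 × 0.229 = 0.38.

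At 19 v 19, unadjusted, equivalence has 80% power (zero true difference, 5% each side) only if the margin is about 0.97 SD. At a margin of 0.5 SD the power is 0.02.

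**4. Illustrate REAR.** The documents give no SD in dB, so a range is assumed. Single signed summary per participant, 19 v 19. The ±3 dB margin in the last column is for illustration only, with zero true difference.

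| Assumed SD | P(true 3 dB difference non-significant) | Equivalence power at ±3 dB |
|---|---|---|
| 3 dB | 0.15 | 0.83 |
| 4 dB | 0.39 | 0.47 |
| 5 dB | 0.56 | 0.15 |

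None of this simulates the planned across-frequency or repeated-measures models.

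**The case against.** **The ±3 dB criterion serves as the margin.** It is the closest thing the plan has, but it governs programming of one fitting and is never tied to the group comparison. It does bear on the likely spread. If every SoC fitting met it, signed SoC deviations at Session 2 could not have an SD above 3 dB. A common SD of 5 dB would then need considerable extra variability at Session 3 or in the experimental group. This stands as a reason to give the 3 dB row most attention, though it does not exclude 4 or 5 dB.

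**Hypothesis 3b never uses the word equivalent.** True. The equivalence claim lies in Aim 3, Hypothesis 3a and the REAR sentence of the analysis section. No sentence says that a non-significant self-report result will be reported as equivalence. The narrower point stands: non-significance confirms Hypothesis 3b as worded, and under an equivalence aim that invites the reading.

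**Stronger readings that the documents do not support.**

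- A reader might infer that VA adoption hangs on the equivalence test. Background section 1b says of the approach that "it may be incorporated in VA practice for some Veterans, and be an additional service", but its condition is that the approach be effective and efficient. Only the Risk/Benefit Assessment ties a consequence to equivalence, and that consequence concerns evidence.
- A reader might infer that the contrast is undefined. Design names the respective SoC fitting; a pooled contrast is nowhere stated.
- A reader might infer that the REAR quantity is undefined. The analysis section uses in situ REARs for the equivalence comparison and derived REARs for meeting targets. Only the wording of Hypothesis 3a is out of line.
- A reader might infer that leaving out a baseline covariate is an error. It is an analyst's choice.

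**Conclusion.** The point holds and needs correcting before Session 3 data are examined. Study 3 states an equivalence aim, plans and sizes difference analyses, and gives no rule by which equivalence could be concluded.

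For self-report the gap is material. At 19 v 19, half an SD would more often than not be missed without baseline adjustment, and still with probability 0.44 at an assumed baseline correlation of 0.7. For REAR the risk is small if the spread is near 3 dB and grows with it. The sizes are illustrative: they rest on one value per participant and on assumed effects, SDs and correlations. The absence of a margin and decision rule rests on the text alone.

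**What to change.** 1. Before Session 3 data are examined, pre-specify and justify a margin for the EXP-open minus SoC-open difference in in situ Session 3 REAR deviation from target. Align the derived wording of Hypothesis 3a with that quantity. Add: *Equivalence will be concluded only if the 90% CI for the difference lies wholly inside the margin.* The ±3 dB and ±5 dB figures may inform the choice but are not ready-made group margins.

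2. Reword Hypothesis 3b in the same way for named self-report scales. Where no margin can be justified, report the difference with its interval and conclude only that no difference was detected. Using the Session 1 score as covariate is an optional gain in precision. The data will exist: "The self-report outcome battery on the current hearing aids will be assessed".

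3. State that the 0.95 in Study 3 Power Analysis is power to detect a difference. Report the power for the chosen equivalence endpoint and contrast at the planned size. More participants are not required for this.

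The cost is wording, a justified margin and one calculation, on data already planned. The downside is that the stated power may look less favourable, and equivalence may not be claimable at the planned size, which would leave an estimate with its interval.

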For Study 2, we are interested in making measures with these non-custom RIC and RITA hearing aids across a variety of ears of representative audiograms of open fit hearing aids. After further consideration, we decided to use the mean audiometric configurations from our previous multisite RR&D Merit Review examining open-fit hearing aids for the current Study 2. The participants do not have to have the actual loss for which we are fitting and verifying in this laboratory-based study, but have hearing loss similar to the audiogram they are assigned to reduce the risk of discomfort.

Vulnerable populations will NOT be recruited.

All studies will continue screen and consent until the targeted sample size of usable data is obtained (accounting for attrition) including 58 Veterans for Study 1; 106 Veterans for Study 2; and 88 Veterans for Study 3. See sample size estimates below.

Subject Recruitment

All subjects will be from the Durham VA audiology clinics. All potential participants will have an equal chance of being selected to participate in the study should they meet the inclusion/exclusion criteria (determined via preliminary chart review). Several recruitment methods will be utilized including through the audiology clinicians, letter, flyers, and signage.

The audiology clinicians will be informed of the study requirements for all three studies. If the clinician thinks the patient is a potential candidate for the study, then the clinician will ask if the patient wants to talk to a member of the study staff to learn more about the study. If the study staff member is available, then s/he will speak to the patient then. They potential participants can be consented at the VA at this time. If not, then the patient will be provided the recruitment letter and flyer and asked to contact the study staff. If the patient would like to be contacted by phone by the study staff, then the clinician will document their agreement to be contacted by phone in the clinical note.

Patients who are experienced hearing aid users scheduled in the audiology clinic to be considered for new amplification may be mailed the recruitment letter and flyer. In addition, Veterans who are eligible for new amplification (i.e., current hearing aids are > 4 years old)

based on a review of the hearing-aid ordering system (ROES) in CPRS, can be mailed a recruitment letter and flyer. These experienced hearing-aid users are required for Study 1 and 3.

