Study 1 Power Analysis. The primary outcome of interest is based on fitting accuracy of each ear (i.e., deviation of REAR from prescriptive target across frequency). A power analysis for a repeated measure ANOVA with an effect size $\eta^2 = 0.10$, power ($1-\beta$) = 0.80, and $\alpha = 0.05$ requires a sample size of 100 ears (total of 50 participants) over the two groups. A small effect size is expected, as a small effect size was found in the preliminary data ($\eta^2 = 0.10$). Considering 15% attrition, then 8 additional participants will be needed ($N = 58$) resulting in 29 participants per group.

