Study 2 Power Analysis. The sample size for this aim is based on having 12 monaural hearing aid fittings (3 manufacturers of 1 open RIC, 1 closed RIC, 1 open RITA, and 1 closed RITA) per participant (ears counterbalanced across participants such that odd-numbered subjects obtain fittings in the left ear and even numbered in the right ear). To ensure a wide range of RECDs and the expected variability in slit leak venting with closed domes, our target sample size is now 96 participants. See randomization Table in Appendix 6 in the grant application for details. For this single session study, we will account for 10% attrition due screen failure and thus will recruit an additional 10 participants for a total of N = 106.

Study 2 Data Analysis. The data from this study will not be analyzed in the usual manner as the purpose of this study is to develop correction factors for open and closed dome fittings of RIC and RITA style hearing aids from several manufacturers. First the frequency-specific gain deviations for each ear as a function of vent size will be calculated. Second, Linear and nonlinear modeling of these data with the goal of developing a best fit model of the relationship between physical vent size and the frequency specific change in gain. The model will also be adjusted as a function of hearing loss, if necessary, to account for cases when the model correction would erroneously lead to negative gain.

Study 3 Power Analysis. A power analysis based on the same expectations as Study 1 regarding fitting accuracy was conducted. For a mixed model repeated measure ANOVA with an effect size $\eta^2 = 0.10$, power $(1-\beta) = 0.80$, and $\alpha = 0.05$ requires a sample size of 100 ears (total of 50 participants) over the four groups, or 13 participants per group. A small effect size is expected, as a small effect size was found in the SPIRE data ($\eta^2 = 0.10$). Nonetheless, considering increased variability due to venting and to obtain robustness required by clinical standards, we will increase the sample size to achieve higher power of $(1-\beta) = 0.95$. This would bring the sample size of ears to 152, or 76 participants in total (19 per group). Considering 15% attrition, then 12 additional participants will be needed (N = 88) resulting in 22 participants per group.

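### Attrition allowances are a percentage of the evaluable target rather than of enrolment, so planned totals fall about one participant short at the stated loss, and the recruitment rule attaches the wrong numbers to usable data

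*Combined protocol and SAP*

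**What the plan says.** All the sizes stand under Data Analysis and Statistical Considerations and are repeated in Selection of Subjects.

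- **Study 1 Power Analysis.** At power 0.80 the calculation "requires a sample size of 100 ears (total of 50 participants) over the two groups". The loss allowance follows: "Considering 15% attrition, then 8 additional participants will be needed", for a total of 58, "resulting in 29 participants per group".
- **Study 3 Power Analysis.** At power 0.95 the number is 152 ears, which is 76 participants or 19 per group. The same step follows: "Considering 15% attrition, then 12 additional participants will be needed", for 88 in total and 22 per group.
- **Study 2 Power Analysis.** No power calculation is given. The size is chosen to cover the spread of RECDs and of slit-leak venting: "our target sample size is now 96 participants". Loss is put at 10% and ascribed to screen failure, and the plan "thus will recruit an additional 10 participants for a total of N = 106".
- **Selection of Subjects.** One rule covers all three studies: screening and consent go on until the target number with usable data is reached, with attrition taken into account. The numbers attached to the rule are the inflated ones: "including 58 Veterans for Study 1; 106 Veterans for Study 2; and 88 Veterans for Study 3".

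**The concern.** An attrition rate is a fraction of the people enrolled. To finish with n evaluable participants after a proportion d is lost, N must satisfy N × (1 − d) = n, so N = n/(1 − d). The plan takes d percent of n and adds it, which gives n × (1 + d). This is always too small, because (1 + d)(1 − d) = 1 − d² is less than 1. All three totals then miss in the same direction, even though each was rounded up.

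Two things depend on this. The first is whether planned enrolment protects the evaluable numbers behind the stated power in Studies 1 and 3, and the chosen coverage in Study 2. The second is whether the team can tell when to stop recruiting. The power sections treat 50, 96 and 76 as the numbers needed, but the stopping rule in Selection of Subjects cites 58, 106 and 88.

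**Working it through.** **Inputs.** Evaluable targets n, attrition d and stated totals N come from the three power sections. The targets are taken as given.

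**Reproducing the plan, then checking it.**

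| Study | n | d | n × (1 + d) | Stated N | Left: N × (1 − d) | Short by | n/(1 − d) | Loss that N covers: 1 − n/N |
|---|---|---|---|---|---|---|---|---|
| 1 | 50 | 15% | 57.5 | 58 | 49.3 | 0.7 | 58.8, so 59 | 13.8% |
| 2 | 96 | 10% | 105.6 | 106 | 95.4 | 0.6 | 106.7, so 107 | 9.4% |
| 3 | 76 | 15% | 87.4 | 88 | 74.8 | 1.2 | 89.4, so 90 | 13.6% |

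Rounding up n × (1 + d) gives every stated total exactly, so the method used is not in doubt.

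**Equal groups.** Study 1: 25/0.85 = 29.4, so 30 per group and 60 in total, against 29 and 58. Study 3: 19/0.85 = 22.4, so 23 per group and 92 in total, against 22 and 88. At 15% loss, 22 per group leaves 22 × 0.85 = 18.7 against 19.

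**Effect on power (illustration only).** The plan's ear counts cannot be fully reproduced, because the number of repeated measures and their correlation are not given. A plain between-group F test is used instead, at η² = 0.10, so f² = 0.10/0.90 = 0.111, with noncentrality N × f² and α = 0.05. Only the change in each row matters; the levels are not the plan's 0.80 and 0.95.

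| Study | Unit | Size at target, then after stated loss | Power |
|---|---|---|---|
| 1 (2 groups) | ears | 100, then 98.6 | 0.910, then 0.906 |
| 1 (2 groups) | one ear per participant | 50, then 49.3 | 0.637, then 0.630 |
| 3 (4 groups) | ears | 152, then 149.6 | 0.941, then 0.937 |
| 3 (4 groups) | one ear per participant | 76, then 74.8 | 0.654, then 0.646 |

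Every fall is below 0.01. Study 2 is left out because it has no power target.

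**The recruitment rule.** The sentence in Selection of Subjects can be read in two ways.

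1. The figures 58, 106 and 88 are enrolment totals. They are then slightly low for the stated attrition, as the first table shows.
2. They are usable-data targets, which is the literal reading. Enrolment at the stated rates would then have to be 58/0.85 = 68.2, so 69; 106/0.90 = 117.8, so 118; and 88/0.85 = 103.5, so 104. None of these matches the totals in the power sections.

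On either reading the two places do not agree.

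**The case against.** The strongest reply is that the recruitment rule already deals with this. If screening and consent continue until enough usable data are in hand, the totals are forecasts and not caps, and no shortfall need occur. If the inflated figures are themselves the usable-data targets, the studies would finish above 50, 96 and 76. This stands, and it removes any claim that the studies will end too small. It does not settle which figure stops recruitment.

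The second reply is scale. The misses are 0.7, 0.6 and 1.2 participants, and the totals lie within one or two of n/(1 − d). The planning rates of 15% and 10% are round figures with no source given, and the loss actually covered differs from them by 1.4 points at most. Chance also outweighs the correction. If participants drop out independently at exactly the stated rates (an assumption), the probability of retaining the target is 0.49, 0.50 and 0.43 with 58, 106 and 88. It is still only 0.61, 0.62 and 0.63 with 59, 107 and 90. The equal-group totals of 60 and 92 give 0.72 and 0.79. All of this stands and makes the point a minor one. The one gap that goes somewhat beyond rounding is Study 3 with four equal groups, 92 against 88.

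The third reply is that Study 2 is a different case. Its loss is screen failure in a single-session study, so 106 is a recruitment count, and no power calculation depends on having 96 rather than 95. This also stands. Only the arithmetic slip is shared.

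**Conclusion.** The formula is wrong in all three studies, and the consequence is small. If the totals were fixed and loss came out exactly as stated, the expected evaluable numbers would be about one participant or less below target, at an illustrative power cost under one percentage point in Studies 1 and 3 and none in Study 2.

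A reader might infer that the enrolment totals fail to deliver the planned power, or that all three studies will finish under size. The documents do not support either inference. The shortfall depends on treating the totals as caps, which Selection of Subjects does not say; the power change is negligible; and Study 2 makes no power claim.

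What needs correcting is consistency. The stated attrition rates are not the rates the totals cover, and the stopping rule attaches to usable data numbers that the power sections use for enrolment. The conclusion takes the evaluable targets and attrition rates as the plan gives them and does not test whether 50 and 76 are themselves adequate.

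**What to change.** In Selection of Subjects, name 50 (Study 1), 96 (Study 2) and 76 (Study 3) as the evaluable targets at which recruitment stops, and give 58, 106 and 88 as planned enrolment.

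In the three power sections, do one of the following:

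- Keep the totals and say that they cover losses of about 13.8% (Study 1), 9.4% (Study 2) and 13.6% (Study 3). Word this as what the totals can absorb, since these percentages are derived from N and are not a new forecast of attrition. No extra participants are needed.
- Keep the 15%, 10% and 15% and restate planned enrolment as n/(1 − d): 59, or 60 with equal groups, for Study 1; 107 for Study 2; and 90, or 92 with equal groups, for Study 3. Carry the same figures into Selection of Subjects. This adds one or two participants in Study 1, one in Study 2, and two to four in Study 3.

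Either way the change is a few lines of text, with no effect on study procedures or on the analysis.
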